8.2 Disposition of Study Subjects

Subject disposition will be summarized in total using counts and percentages. The number and percentage of subjects in the FAS who completed and discontinued will be tabulated along with the specific reasons for discontinuation.

8.3 Demographic and Baseline Characteristics

Summary statistics of subject demographics (age, sex, race, and ethnicity) will be presented for the FAS. Vital signs (height, weight, body mass index, systolic blood pressure, diastolic blood pressure, heart rate and ASA score) will be summarized in a similar manner.

Counts and percentages will be provided for medical history terms included on the Relevant Medical History eCRF including Diabetes, Recently on blood thinners, Prior history of stone disease, Anatomic abnormalities, and Prior urinary tract infections. Data collected in the Other Relevant Medical History and Urologic or Other Relevant Procedure History eCRFs will be listed.

Summary statistics will be provided for quantitative parameters collected in the Complete Blood Count (CBC) and Complete Metabolic Panel (CMP) blood draws reported at the Screening/Baseline Visit. Urinalysis and culture test results will be listed.

8.4 Clinical Characteristics

Pre-operative clinical characteristics as well as procedure day measurements will be summarized at both the subject level as well as the kidney stone level given that many subjects present with more than one stone for treatment in the study. At the subject level, counts and percentages will be provided for whether the left or right kidney is being treated, as well as the number of stones per subject, and the number of kidney regions with stones. Summary statistics will be provided for cumulative stone burden, defined as the sum of the longest dimension of all stones, estimated percutaneous tract length, subject weight prior to the procedure and oxygen saturation as reported in the Pre-Procedure Setup eCRF. At the stone level, counts and percentages will be provided for the pole location and sublocation and summary statistics will be provided for the longest linear dimension, as well as the remaining dimensions in decreasing order, and stone radio density.

8.5 Primary Endpoint and Associated Hypotheses

No formal hypotheses are specified for this study.

The primary endpoint is the successful completion of the robotic-assisted mini-PCNL kidney stone removal procedures including:

- Gaining safe concomitant (i.e., retrograde and antegrade) access to the upper urinary tract
- Locating and visualizing the kidney stones
- Enabling fragmentation of stones by standard of care method
- Evacuating stone fragments and dust

Successful completion is identified by answering "Yes" to each of these questions on the Investigator Assessment form. The number and percentage of subjects experiencing successful completion will be summarized and an exact 95% confidence interval will be estimated. Counts and percentages will also be provided for each of the four components of the primary endpoint.

8.6 Secondary Endpoints and Associated Hypotheses

There are no secondary endpoints specified in the study protocol. Analysis of additional data collected is described in subsequent sections.

8.7 Additional Endpoints

Summary statistics will be provided for the following:

- Procedure duration: defined as the difference between "When was the patient's percutaneous wound closed?" from the Mini-PCNL eCRF and "When is the Cystoscope introduced?" from the Pre-Procedure Setup eCRF
- Cumulative stone burden at the 30-day follow-up visit as well as change in stone burden from the Screening/Baseline visit; Change in cumulative stone burden (%) will also be summarized and is defined as 100*(Change/Baseline)
- Stone radio density at 30 days
- Duration of stent placement in days: defined as the difference between "Date of stent extraction" from the Physical Exam and Vital Signs eCRF at the 30-day visit and "Did you place a ureteral stent in this patient?" from the Mini-PCNL eCRF + 1
- Subject weight post-procedure as well as change from pre-procedure weight
- Length of stay in nights: defined as "Date of hospital discharge" "Date of hospital admission"
- CBC and CMP results at the 30-day visit as well as change from the Screening/Baseline visit

• Selected labs taken immediately post procedure (sodium, creatinine, hematocrit) as well as change from the Screening/Baseline visit

Counts and percentages will be provided for the following:

- Conversion to conventional (non-robotic) treatment methods from the Investigator Assessment eCRF
- At the subject level, the number, location, individual sizes of post-operative stones, and cumulative stone burden of any post-operative stones will be provided.
- Estimated stone free rate at 30 days: defined as the number of subjects with no reportable stone size (or size reported as zero in all three dimensions) on the Radiology Imaging II eCRF at the 30-day visit
- Number of Randall's plaques in each of the Upper Pole, Interpole, and Lower Pole as reported in the Investigator Assessment eCRF
- Subjects requiring retreatment for stone removal with the duration of the study, as reported within the Concomitant Procedure eCRF

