8.10 Handling of Missing Data

All summaries will be performed only on subjects undergoing the scheduled procedure and only observed data will be summarized. There will be no imputation of data for early terminated subjects or for missing data within the database.

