8.15 Exploratory Analyses

Protocol: URO-2021-0001 SAP Version 1.0, 08DEC2023 Page 12 of 14

Protocol: URO-2021-0001 SAP Version 1.0, 08DEC2023

9 Data Monitoring Committee (DMC)

No Data Monitoring Committee was planned or utilized during this study.

End of Document

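### Does the 30-day change in stone burden need a volume measure because it is built only on longest dimensions?

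*SAP*

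**What the plan says.** SAP 8.4 (Clinical Characteristics) sets the definition: "cumulative stone burden, defined as the sum of the longest dimension of all stones". It summarises clinical characteristics by subject and by stone, "given that many subjects present with more than one stone for treatment in the study". At the stone level, "summary statistics will be provided for the longest linear dimension, as well as the remaining dimensions in decreasing order".

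SAP 8.7 (Additional Endpoints) summarises that burden at 30 days and its change from Screening/Baseline, then adds the relative change: "Change in cumulative stone burden (%) will also be summarized and is defined as 100*(Change/Baseline".

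The same section gives further results on residual stone. At the subject level, "the number, location, individual sizes of post-operative stones, and cumulative stone burden of any post-operative stones will be provided". The stone-free rate at 30 days is "defined as the number of subjects with no reportable stone size (or size reported as zero in all three dimensions", and retreatments are counted. SAP 8.10 adds that "only observed data will be summarized", without imputation.

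No volume measure appears in the text that can be read. Under the heading "8.15 Exploratory Analyses" no body text is shown, so what that section contains is unknown.

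**The concern.** Lithotripsy turns one stone into several pieces, and suction then takes the pieces away (Protocol 4.2, Lithotripsy & Removal). Total length is not conserved when a stone breaks, whereas total volume is. In a subject with several measurable residual fragments, the percent change in summed length therefore reflects both how finely the stone was broken and how much was removed. The same value could describe a stone left whole or stones almost entirely cleared.

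Protocol 3 makes clearance of visible debris an aim, and Protocol 4.2 has the follow-up CT measure what remains. A reader could thus take a modest, flat or positive value as poor clearance when most of the stone is gone. All three dimensions seem to be recorded at both visits, so a volume row looked like an easy omission to repair.

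**Working it through.** The documents state no figure for stone-burden change, so there is nothing to reproduce. The check has two parts: whether the geometry is right, and whether the plan's other results resolve the ambiguity.

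**Inputs.** From the documents: burden is the sum of longest dimensions (SAP 8.4); percent change is 100 × change / baseline (SAP 8.7); entry requires stones of at least 10 mm (Protocol 5.1); enrolment is at most 20 (SAP 1.2). Assumed for illustration only: spherical stones and the sizes below.

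**Formulas.** With baseline diameters b and residual diameters r:

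- length change = 100 × (Σr − Σb) / Σb
- volume change = 100 × (Σr³ − Σb³) / Σb³

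| Baseline (mm) | Residual at 30 days | Length change | Volume change |
|---|---|---|---|
| 20 | five of 4 | (20 − 20)/20 = 0% | (320 − 8000)/8000 = −96.0% |
| 20 | two of 10 | (20 − 20)/20 = 0% | (2000 − 8000)/8000 = −75.0% |
| 20 | one of 7 | (7 − 20)/20 = −65% | (343 − 8000)/8000 = −95.7% |
| 10 + 10 | one of 10 | (10 − 20)/20 = −50% | (1000 − 2000)/2000 = −50% |
| 10 + 10 | five of 2 | (10 − 20)/20 = −50% | (40 − 2000)/2000 = −98% |
| 15 + 10 | five of 5 | (25 − 25)/25 = 0% | (625 − 4375)/4375 = −85.7% |
| any | none | −100% | −100% |

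So the geometric point is true. The length change alone cannot tell rows 1 and 2 apart, nor rows 4 and 5.

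**Does the plan leave it at that?** The second column of the table is information SAP 8.7 already provides for each subject: how many residual stones there are, where they lie and how large each is. Rows 1 and 2 differ as five stones of 4 mm against two of 10 mm; rows 4 and 5 as one of 10 mm against five of 2 mm. With no more than 20 subjects, these results can be read one by one. The last row, complete clearance, is the same on either scale, so only subjects with residual stone are affected.

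**Is the linear scale out of place?** No. Protocol 2.1 describes treatment thresholds as total stone burden in millimetres, and Protocol 5.1 sets entry size in millimetres. The change measure uses the same kind of unit.

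**Would volume be the clearer measure?** Not uniformly. Rows 1 and 3 give −96.0% and −95.7% by volume, which are almost indistinguishable; by length they are 0% and −65%. Against an aim of clearing all visible debris, five 4 mm residuals are a failure. The length row shows that, while a volume row would report a 96% reduction.

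**Effect on the summary.** Suppose 19 of 20 subjects are cleared and one is as in row 1. The mean length change is (19 × −100 + 0)/20 = −95%. The mean volume change is (19 × −100 − 96)/20 = −99.8%. The median is −100% for both. The gap of 4.8 percentage points in the mean comes from one assumed subject, whose residual stones would be reported individually.

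**The case for a change.** The best argument for the concern is that subject-level details are not a summary. The stone-free rate is yes or no, so the change in burden is the only visible summary that grades partial clearance, and it blends two steps that the primary endpoint keeps apart. Adding volume would cost one derived variable, and the length row would stay.

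Much of this is fair. The length change does depend on the number of fragments, and a careful report should read it beside the count and sizes. But that calls for sensible presentation of results already planned; it does not show that the plan is wrong. The documents do not indicate how often subjects will have several measurable fragments, and Protocol 4.2 has the kidney inspected endoscopically for residual fragments at the end of the procedure. A volume row would also be chosen after the three data summaries acknowledged in SAP 8.9, would tend to look more favourable, and would lose any subject with an incompletely measured fragment if volume requires all three dimensions. Protocol 4.1 lists stone removal efficiency among the data collected, and the unseen exploratory section may cover it; text that is not shown cannot be counted as absent.

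A related worry is whether a blank size at 30 days means zero or missing. Read with SAP 8.10, the ordinary answer suffices: a CT showing no stone gives an empty sum, which is zero, and no CT gives a missing value.

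**Conclusion.** The concern does not stand. The geometry is correct, but no number, rule or conclusion in the plan is wrong: the measure is defined, computable, consistently applied and in the protocol's own unit. The ambiguity is resolved by residual-stone details reported in the same section for at most 20 subjects.

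Nothing inferential is at stake. This is an additional descriptive endpoint without a hypothesis, and the primary endpoint, its exact 95% interval and the safety summaries do not use it. In the illustration, one multi-fragment subject in 20 moves the mean by 4.8 points and the median not at all.

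This conclusion assumes that the subject-level number and sizes of residual stones are reported as SAP 8.7 states. The spheres and the cohort are illustrative assumptions, not trial figures. A volume row would be a matter of preference.

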#### Follow-up

The subject will have 1 follow-up visit and have procedures completed as outlined in Table 1.

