## 9.1 Interval Windows

Interval windows for the purpose of analysis in this study will not be defined outside of those already specified in the protocol for visit scheduling. The final visit occurs approximately 30 days after surgery, thus no interval windows need to be defined given the absence of long-term follow-up in this study. The Schedule of Assessments specifies a window of 7 days around the scheduling of the 30-day follow-up visit, and any information entered in the eCRFs at this visit will correspond to the 30-day visit. There will be no assigning of observations to time points outside of the visit to which they are recorded in the eCRFs.

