1.2 Study Design

This is a single-center, prospective, single-arm study to collect descriptive data on the roboticassisted mini-PCNL removal of kidney stones using the MONARCH[™] system.

The study will enroll up to 20 patients. Each enrolled subject will be followed up to 30 days \pm 7 days post procedure.

2 Treatment Assignment

This is a single-arm study where all enrolled subjects will have the MONARCH[™] system utilized for removal of kidney stones via a mini-PCNL procedure.

3 Randomization and Blinding Procedures

As this is a single-arm study, no randomization occurred, and no blinding procedures are required.

4 Interval Windows

Interval windows for the purpose of analysis in this study are not defined outside of those already specified in the protocol for visit scheduling where the collection of data for the primary and safety endpoints occurs.

Table 1 Schedule of Assessments in the protocol specifies the following visit windows:

- Screening/baseline: approximately 30 days prior (allowing up to 60 days prior) to the procedure
- Pre-operative imaging, no longer than 30 days pre-procedure
- Post-operative 30 days follow-up (± 7 days)

Any information entered in the electronic Case Report Forms (eCRFs) at a given visit will correspond to the scheduled visit. There will be no assigning of observations to time points outside of the visit to which they are recorded in the eCRFs.

5 Levels of Significance

No hypotheses are specified for this study and no p-values are being calculated, therefore no level of significance is specified. All estimation of endpoints will be performed using 95% confidence intervals where indicated below.

6 Analysis Sets

The summary of all performance and safety endpoints will be performed on the set of subjects in whom the MONARCHTM system is utilized during the procedure. This will be labeled as the Full Analysis Set (FAS) and will be identified by having a time recorded in the "When was the Ureteroscope introduced (timestamp)?" field on the Procedure: Ureteroscopy and Percutaneous Access eCRF.

7 Sample Size Justification

The study is expected to enroll up to 20 subjects. No formal hypothesis is being tested and therefore the sample size determination is not based on a statistical power calculation, but rather is deemed sufficient for a descriptive summary of safety and primary endpoints in this first-in-human experience with the study device.

8 Analyses to be Conducted

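### SAP 8.7 computes stent duration only where the 30-day form carries an extraction date, so any stent still in place at that visit is dropped and the mean and maximum come out short.

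*SAP*

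**What the plan says.** SAP 8.7 lists the item among the additional endpoints that get summary statistics: "Duration of stent placement in days: defined as the difference between" two form entries, plus 1.

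- The later entry is the date of stent extraction, taken "from the Physical Exam and Vital Signs eCRF at the 30-day visit".
- The earlier entry is the Mini-PCNL eCRF item "Did you place a ureteral stent in this patient". No placement date is named.

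These rules apply to it:

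- SAP 8.10: "only observed data will be summarized", and "There will be no imputation of data for early terminated subjects or for missing data within the database".
- Protocol 4.2, Follow-up: "The subject will have 1 follow-up visit and have procedures completed as outlined in Table 1".
- Protocol 9.1: "The Schedule of Assessments specifies a window of 7 days around the scheduling of the 30-day follow-up visit".
- SAP section 4 (Interval Windows): "There will be no assigning of observations to time points outside of the visit to which they are recorded in the eCRFs".

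SAP 8.7 also lists items to be reported as counts and percentages: conversion, post-operative stones, stone-free rate, Randall's plaques and retreatment. The number of subjects stented and the number with a stent still in place are not on that list. SAP 8.12 plans no sensitivity analysis.

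**The concern.** Whether a subject contributes a duration depends on the duration itself. A stent removed before or at the 30-day visit has an end date; one that stays longer does not. The SAP says nothing about the second kind: it gives no censoring rule, no count and no later update of the date. The reported duration would then describe early removals while reading as a description of all stented subjects. In a study of up to 20 patients, one or two omitted long placements can move the mean and change the maximum substantially.

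The start of the interval is also loosely written. The other intervals in SAP 8.7 (procedure duration, length of stay) run between named times or dates. This one starts at an item worded as a yes/no question.

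**Working it through.** **Plan's own figure.** There is none to reproduce. The documents give no stenting rate, planned dwell time, removal schedule or expected share of stents in place at day 30. Every number below except the visit window and the sample size of 20 is an assumption.

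**Step 1: follow one subject through the rules.** Suppose a stent is in place at the 30-day visit. The extraction date on that visit's form is blank, the difference cannot be formed, nothing is imputed, and there is no second visit. The subject leaves the summary. This follows from reading SAP 8.7 and 8.10 together; neither states it outright. A subject who exits before the visit is lost in the same way.

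**Step 2: ceiling on what can be recorded.** If extraction is on or before the visit, the largest value is visit day + 1: 23 + 1 = 24, 30 + 1 = 31, or 37 + 1 = 38 days.

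**Step 3: arithmetic illustration.** Assume 20 stented subjects and a visit on day 30. The removed stents all came out on day 10 (duration 10 + 1 = 11), and k stents are still in, counted only to the visit (30 + 1 = 31).

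Mean over all stents = ((20 − k) × 11 + k × 31) / 20. The plan reports 11 in every row.

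| k still in | mean, at least | reported value short by, at least |
|---|---|---|
| 0 | 220/20 = 11.0 | 0.0 |
| 1 | (209 + 31)/20 = 12.0 | 1.0 |
| 2 | (198 + 62)/20 = 13.0 | 2.0 |
| 4 | (176 + 124)/20 = 15.0 | 4.0 |
| 6 | (154 + 186)/20 = 17.0 | 6.0 |

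The shortfall is k × (31 − 11)/20 = k days, a lower bound. If the retained stents truly lasted 60 days, it would be k × (60 − 11)/20 = 2.45k days, or 2.45 for one stent and 4.9 for two. For k of 1 or more, the reported maximum is 11 against at least 31.

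The median does not move here. At least 14 of 20 durations equal 11, so it is 11 with or without the retained stents. A Kaplan-Meier curve drops at day 11 to k/20 (0.05, 0.10, 0.20 or 0.30), so its median is also 11.

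**Step 4: spread-out durations.** I assumed lognormal dwell times and a visit day uniform on 23 to 37, dropped stents still in at the visit, and used 400,000 draws. Means and medians include the + 1.

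| median dwell, log-SD | still in | mean, all / removed only | median, all / removed only |
|---|---|---|---|
| 7 days, 0.3 | 0.0% | 8.3 / 8.3 | 8.0 / 8.0 |
| 10 days, 0.5 | 1.8% | 12.3 / 11.9 | 11.0 / 10.9 |
| 14 days, 0.5 | 7.3% | 16.9 / 15.3 | 15.0 / 14.4 |
| 21 days, 0.5 | 25% | 24.8 / 19.3 | 22.0 / 18.9 |

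The mean is never overstated in these runs. Its shortfall goes from nil to 24.8 − 19.3 = 5.5 days.

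**Step 5: chance that the problem arises.** With 20 stented subjects and a true share p still in, the chance of at least one is 1 − (1 − p)^20: 18% for p = 1%, 64% for 5% and 88% for 10%.

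**The case against.** The strongest reply is that the bias is hypothetical. If all stents are out by the visit, including on the visit day, nothing is lost. That stands: a reader might infer that the reported duration is certainly biased short, and the documents do not support that. They support only that a retained stent would be dropped. Protocol 8.1 names a forgotten stent among known procedure-related events, so the case is foreseen, but no frequency is given.

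A reader might also infer that the endpoint cannot be computed. That goes too far. The start item sits on the procedure form, Protocol 4.1 collects timestamps by procedure phase, and the eCRF item may carry a date that the SAP does not cite. An analyst would use the procedure date, so alone this is a clerical defect. The + 1 is an ordinary inclusive day count.

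Nor is the median necessarily affected. Step 3 leaves it unchanged; step 4 moves it by 0.1 to 3.1 days when some stents remain.

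The exclusion is not wholly invisible. Protocol 9.5 reports the number of subjects for each continuous variable and promises summaries of additional data, which under Protocol 4.1 include stent placement. The number stented minus the number with a duration would show a gap, though not its cause. The listing of concomitant procedures in SAP 8.8 may help case by case. I could not see the SAP text just before 8.2, so I do not claim that no general convention exists.

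Finally, no text forbids entering an extraction date on the form after the visit, and the protocol's Study Exit section allows continued follow-up where a condition requires it. The day 23 to 37 cut-off is therefore an inference, though the natural one.

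**Conclusion.** The point holds in a limited form. As written, a stent still in place at the only follow-up visit yields no duration, and the subjects dropped are those with the longest placements. With a common visit day, every dropped stent outlasts every recorded one, so the mean and maximum fall short. With visits spread over the window an exception is conceivable, but only if many removals cluster near the visit.

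The size runs from zero, if all stents are out, to several days. Under the step 3 assumptions it is at least 1.0 day on the mean per retained stent. This rests on the form being completed at the visit and not updated later, and on retained stents occurring at all, which the documents leave open.

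Some might call this informative censoring, but the plan censors nothing: it leaves out subjects without an end date. Severity is low. This is a descriptive additional endpoint with no hypothesis, neither primary nor safety.

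**What to change.** In SAP 8.7:

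1. Name the stent placement date (the procedure date) as the start, in place of the yes/no item.
2. Report the number of subjects stented, the number removed by the 30-day visit and the number still in place, plus any with unknown status after early exit.
3. Either treat stents still in place as censored at the visit date and give a Kaplan-Meier median, or keep the simple summary and label it as restricted to stents removed by the 30-day visit.

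The counts matter most, because the median may barely change. Kaplan-Meier assumes that the visit date is unrelated to how much longer the stent would stay, which is reasonable for a scheduled visit. If every stent is out, it returns the ordinary median.

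The cost is a few SAP sentences and a little more analysis. The data needed are the procedure date, the visit date and stent status at the visit. The reported duration may look longer.
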